- PK serum sampling
- Review of concomitant medications
- AE assessment

6.2.2.5. Day 57

On Day 57 (± 3 days), subjects will undergo the following assessments:

- C-SSRS (Since Last Visit version)
- Vital signs
- Clinical laboratory tests:
 - Blood chemistry and hematology
 - Urinalysis
 - Coagulation
- PK serum sampling
- ADA serum sampling
- Note: Residual and unused serum and CSF (if applicable) samples will be stored for future use for the measurement of biomarkers Possible LP. INR/ PT/PTT and platelet results within 2 days prior to the LP must be confirmed and determined to be within normal range before LP.
 - Post LP, subjects will remain supine for a minimum of 4 hours, and may be kept longer for observation at the discretion of the Investigator. After the 4-hour observation period, safety and tolerability will be assessed and subjects will be discharged home
- Review of concomitant medications
- AE assessment

6.2.2.6. Day 85

On Day 85 (± 4 days), subjects will undergo the following assessments:

- C-SSRS (Since Last Visit version)
- Symptom directed physical examination
- Neurologic examination
- Vital signs
- Weight
- 12-lead ECG
- Pregnancy test (non-post-menopausal women only)
- Urine drug, urine cotinine, and serum alcohol screen

- Clinical laboratory tests:
 - Blood chemistry and hematology
 - Urinalysis
 - Coagulation
- PK serum sampling
- ADA serum sampling
- Note: Residual and unused serum and CSF samples (if applicable) will be stored for future use for the measurement of biomarkers Possible LP. INR/ PT/PTT and platelet results within 2 days prior to the LP must be confirmed and determined to be within normal range before LP.
 - Post LP, subjects will remain supine for a minimum of 4 hours, and may be kept longer for observation at the discretion of the Investigator. After the 4-hour observation period, safety and tolerability will be assessed and subjects will be discharged home
- Review of concomitant medications
- AE assessment

6.2.3. Optional Follow-Up Visit – Day 120

The Day 120 visit (\pm 7 days) is optional. Subjects who elect to participate in the Day 120 visit will undergo the following assessments:

- PK serum sampling
- ADA serum sampling
- Note: Residual and unused serum samples will be stored for future use for the measurement of biomarkers

6.3. Early Termination

If a subject cannot complete the entire study, efforts will be made to collect all prespecified assessments for Day 85 (Appendix 1), if possible. If a subject withdraws consent before early termination no further procedures should be performed and no additional data should be collected. The Sponsor may retain and continue to use any data collected before the withdrawal of consent.

PMN310 Confidential

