
Reference Therapy, Dose and Mode of Administration:	Placebo will consist of 100 mL 0.9% NaCl and will be administered as a matching single IV infusion over 60 minutes, followed by a 15 minute 0.9% NaCl flush.			
Duration of Study:	Enrolled subjects are expected to be in the study for approximately 16 weeks including a screening period (up to 4 weeks), an inpatient single dose and observation period (5 days), and a postdose outpatient follow-up period (12 weeks). Subjects may return 5 weeks after completion of the postdose outpatient follow-up period for an optional follow-up visit.			
Criteria for Evaluation:	 Vital signs MRI evaluations will be performed at Screening for all subjects and at Day 43 for subjects ≥ 50 years of age to assess for amyloid-related imaging abnormalities (ARIA). If ARIA is detected, MRIs will be repeated every 3-4 weeks until there is resolution, regardless of whether or not the subject is symptomatic. MRIs will be read at an independent central reading laboratory after screening of the first two sentinel subjects for Cohort 1 (age < 50) who will have MRIs performed and read locally. Sequences will include: MRI T2-weighted fluid-attenuated inversion recovery (T2/FLAIR) sequence to detect amyloid-related imaging abnormalities characterized by vasogenic edema or sulcal effusions (ARIA-E) MRI gradient recalled echo (GRE) sequence to detect amyloid-related imaging abnormalities characterized by parenchymal microhemorrhages or sulcal/leptomeningeal hemosiderin deposits (ARIA-H) Diffusion weighted imaging (DWI) sequence can help differentiate ARIA-E from potential cytotoxic edema as may be noted with an incidental acute to subacute infarct ECGs Laboratory test results Physical examinations Neurologic examinations Neurologic examinations Neurologic examinations AEs/serious adverse events (SAEs) Serum ADA C-SSRS Pharmacokinetic: Serum PMN310 concentrations will be measured throughout the study to characterize standard PK parameters using non-compartmental methods (e.g., C_{max}, T_{max}, AUC_{0-e}, t_{1/2}, Vd, and CL) CSF will be collected for drug concentrations 			

Biomarkers and ADAs

 Serum and CSF samples will be obtained for measurement of biomarkers and serum samples for ADAs

Exploratory

- Incidence and titers of ADAs
- Residual and unused serum and CSF samples will be stored for future use for the measurement of biomarkers

Statistical Methods:

Determination of Sample Size

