3.1.1. Dose Escalation Rules

[figure not shown]
Each dose cohort will consist of 8 subjects (6:2; PMN310:placebo). To evaluate the short term safety and tolerability of PMN310, each cohort will enroll a sentinel group of 2 subjects (1:1, PMN310:placebo) who will be dosed prior to dosing the remaining 6 subjects in the cohort (5:1, PMN310:placebo). The first two sentinel subjects for Cohort 1 (age < 50) will have MRIs performed and read locally. The SRC will review all safety data collected through 48 hours postdose from the 2 sentinel subjects to determine the acceptability of proceeding with dosing of the remaining 6 subjects in the cohort. Additional details on the SRC are provided in Section 3.1.2.

Dose escalation to the next cohort will only occur after approval by the SRC. The SRC will determine the acceptability of proceeding with enrollment of the next cohort based on review of safety and any available PK data at the time of review through 7 days postdose for a minimum of 6 of 8 subjects per cohort. Doses to be evaluated are presented in Section 5.2.1.

In the event that important safety concerns are observed at any time during the study, administration of study drug will be paused, subjects in the subsequent cohort(s) will not receive further study drug until further review of the safety data has occurred, and subsequent recommendations and approval have been provided by the SRC. Dose escalation/stopping rules are detailed in Section 5.5.

A schematic illustrating the study design is provided in Figure 1.

Figure 1: PMN310-101 Study Schema Per Cohort

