8.2. Removal or Early Withdrawal of Subjects from Therapy or Assessment

8.2.1. Removal of Subjects from Therapy or Assessment

Subjects are free to withdraw from the study at any time, without prejudice to their continued care.

The Sponsor or its designee must be notified if a subject is withdrawn from study treatment or from the study. The reason for withdrawal must be documented in the subject's medical records and CRF.

Subjects who withdraw from treatment prematurely should complete an Early Termination Visit (Section 6.3) as soon as possible.

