9.3. Analyzed Population Sets

- The safety population will include all subjects who receive study drug.
- The PK population will include all subjects who receive study drug and have at least 1 sample for PK analysis.
- The evaluable population will include all subjects who complete at least 1 postdose LP.

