9.4. Statistical Analyses

9.4.1. Safety Analysis

Only subjects in the safety population will be included in the safety analysis. Safety and tolerability results including vital signs, MRI if/when indicated, ECGs, laboratory test results, physical and neurological examinations, AEs/SAEs, serum ADA, and C-SSRS from this study will be assessed using summary statistics by cohort (e.g., n, mean, median, minimum, maximum, for continuous endpoints; n and percentages for binary and categorical endpoints). All placebo subjects from the different cohorts will be combined into a single group for summary purposes.

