11.3. Protocol Revisions and/or Deviations

Substantive changes in the protocol include changes that affect the safety of subjects or changes that alter the scope of the investigation, the scientific quality of the study, the experimental design, dosages, assessment variable(s), the number of subjects treated, or the subject-selection criteria. Such changes must be prepared as a protocol amendment by the Sponsor and implemented only upon joint approval of the Sponsor and the Investigator. A protocol amendment must receive IRB/IEC approval before implementation. In parallel with the IRB/IEC approval process, the protocol amendment will be submitted to the appropriate regulatory authority as an amendment to the regulatory submission under which the study is being conducted. If a protocol amendment requires changes in the ICF, the revised ICF prepared by the Investigator also must be approved by the Sponsor, Medical Monitor, and the IRB/IEC before implementation.

Departures from the protocol are allowed only in situations that eliminate an immediate risk to a subject and that are deemed crucial for the safety and wellbeing of that subject. The Investigator or the attending physician also will contact the Medical Monitor as soon as possible in the case of such a departure. These departures do not require preapproval by the IRB; however, the IRB and Medical Monitor must be notified in writing as soon as possible after the departure has been made. In addition, the Investigator (or designee) will document in the subject's CRF the reasons for the protocol deviation and the ensuing events.

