- ⁶ Vital signs should always be collected up to 45 minutes before PK sampling (i.e., nominal time) unless otherwise indicated before infusion, at the end of infusion (see Section 5.2.1 for a definition for complete infusion), and at 0.5, 1, 2, 4, 8, and 12 hours after the end of infusion. Day 2 (24 and 36 hours), D3 (48 hours), and Day 4 (72 hours), Days 8, 15, 29, 43, 85. Subjects should be resting supine for at least 5 minutes before the vital sign assessment; the exact time of assessment is to be recorded.
- Only subjects ≥ 50 years of age will have MRI assessments at Day 43. If ARIA is detected, repeat MRIs will be performed every 3-4 weeks until ARIA is resolved.
- ⁸ ECGs should always be performed up to 45 minutes before PK Sampling (i.e., nominal time) unless otherwise indicated before infusion, at the end of infusion, and at 1, 2, 4, 8, and 12 hours after the end of infusion. Day 2 (24 and 36 hours), D3 (48 hours), and Day 4 (72 hours), Days 8, 29, and 85.

Date of discharge from the inpatient study clinic is at the discretion of the Investigator. It may be extended, if needed, and is dependent on the need for further observation and/or care.

PMN310-101 Version 1.0, 10 March 2023

- ⁹ FSH will be evaluated for post-menopausal women only. Post-menopausal status will be confirmed through testing of FSH levels (≥ 40 IU/mL).
- ¹⁰ Pregnancy test is not required for post-menopausal women. Serum human chorionic gonadotropin at Screening and urinary chorionic gonadotropin thereafter. If a urine pregnancy test is positive, a serum pregnancy test must be obtained. Additional details provided in Section 7.1.9.
- ¹¹ Pharmacokinetic blood sampling for serum PMN310 concentrations should be performed as follows:
 - Day 1: before infusion, at the end of infusion, and at 0.5, 1, 2, 4, 8, and 12 hours after the end of infusion
 - o Acceptable windows for PK sampling are as follows (exact time of PK collection is to be recorded):
 - Pre-dose sample to be collected within 60 minutes prior to dosing
 - 0.5 to 4-hour post-dose samples to be collected \pm 5 minutes
 - 8 to 12-hour post-dose samples to be collected \pm 10 minutes
 - Day 2 (24 and 36 hours)
 - Acceptable window for PK sampling is ± 30 minutes (exact time of PK collection is to be recorded)
 - Day 3 (48 hours) and Day 4 (72 hours)
 - \circ Acceptable windows for PK sampling are \pm 60 minutes (exact time of PK collection is to be recorded)
 - Days 8, 15, 29, 43, 57, 85

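### A subject aged 50 or over who leaves before the Day 43 MRI can attend the early-termination visit and still have no scheduled post-dose ARIA scan

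*Protocol*

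**What the plan says.** Protocol Section 7.1.7 schedules MRI at Screening for everyone and at Day 43 for subjects aged 50 or over. Footnote 7 of Appendix 1 repeats the rule: "Only subjects ≥ 50 years of age will have MRI assessments at Day 43". Further scans follow only once ARIA has been found. In that case the Synopsis (Criteria for Evaluation) states that "MRIs will be repeated every 3-4 weeks until there is resolution, regardless of whether or not the subject is symptomatic".

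For early leavers, Section 8.2.1 says that subjects who stop treatment prematurely "should complete an Early Termination Visit (Section 6.3) as soon as possible". Section 6.3 defines what that visit contains: "efforts will be made to collect all prespecified assessments for Day 85 (Appendix 1), if possible". It also rules out any procedure once consent is withdrawn. Appendix 1 and SAP Table 1 both label the Day 85 column as Week 12/ET.

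Section 9.4.1 includes "MRI if/when indicated" among the safety results to be summarised. SAP 8.7 plans by-subject listings of MRI results and no summary table.

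**The concern.** The plan intends one post-dose ARIA scan for every subject aged 50 or over. Because the exit visit is defined as a copy of Day 85, it brings back the neurologic examination, ECG, laboratory tests, PK and ADA samples and AE review. It loses the MRI, which belongs to an earlier visit. The documents give no reason for the omission.

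At stake is the safety information on a consenting subject who is on site. The Synopsis wording on repeat scans recognises that ARIA can be present without symptoms. An examination and AE questioning may not reveal ARIA of that kind, and the Day 43 scan is the one planned assessment that would. Several exits listed in Sections 8.2.1.1 and 8.2.2 do not involve withdrawn consent: an intolerable AE, an intercurrent illness, a significant laboratory abnormality, or a decision by the sponsor. A subject who leaves because of an AE is one in whom the scan would be especially informative.

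**Working it through.** **Reading the schedule**

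| Source | Where MRI is marked or listed | MRI at Day 85 / ET? |
|---|---|---|
| Protocol 7.1.7 | Screening; Day 43 if aged 50 or over; repeats if ARIA is found | No |
| Protocol 6.2.2.6 (Day 85 list) | Not listed | No |
| Protocol 6.3 | Refers to Day 85 | No |
| Protocol Appendix 1, MRI row | 2 of 13 visit columns: Screening and Day 43 | No |
| SAP Table 1, MRI row | Screening and Day 43 | No |

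Scheduled post-dose scans for a subject aged 50 or over are therefore one (plus repeats if ARIA is found) if Day 43 is completed, and none if the subject leaves before it and attends the exit visit.

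**How many subjects**

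The plan gives no figure to reproduce. It states no age mix, dropout rate, consent-withdrawal share or attendance rate, so the four rates below are assumptions.

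*PMN310 subjects who could be aged 50 or over.* Six per cohort gives 24 in Cohorts 1 to 4, or 30 with optional Cohort 5. The Cohort 1 sentinels are under 50: "The first two sentinel subjects for Cohort 1 (age < 50) will have MRIs performed and read locally". Sentinels are allocated 1:1, so one of the two receives PMN310.
- 24 − 1 = 23, or 30 − 1 = 29.

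*Share aged 50 or over (assumed 1/6 to 1/3).* Ages spread evenly over 18 to 65 give 16 of 48 years = 1/3. A younger volunteer mix is represented by 1/6.
- 23 × 1/6 = 3.83 to 29 × 1/3 = 9.67 subjects.

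*Leaving before Day 43 (assumed 5% to 10%).*
- 3.83 × 0.05 = 0.19 to 9.67 × 0.10 = 0.97 subjects.

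*Still consenting (assumed one half).*
- 0.19 × 0.5 = 0.10 to 0.97 × 0.5 = 0.48 subjects, if all attend and accept the MRI.
- Chance of at least one: 1 − (1 − 1/6 × 0.05 × 0.5)^23 = 0.09 to 1 − (1 − 1/3 × 0.10 × 0.5)^29 = 0.39.

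*Attending and accepting an MRI (assumed 50% to 80%).* Attendance cannot be taken for granted, since Section 6.3 asks only for efforts.
- 0.10 × 0.5 = 0.05 to 0.48 × 0.8 = 0.39 subjects (unrounded products 0.048 and 0.387).
- Chance of at least one: 1 − (1 − 1/6 × 0.05 × 0.5 × 0.5)^23 = 0.05 to 1 − (1 − 1/3 × 0.10 × 0.5 × 0.8)^29 = 0.32.

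*Consent share varied from 25% to 75%, with full attendance and acceptance.*
- 0.19 × 0.25 = 0.05 to 0.97 × 0.75 = 0.73 subjects.

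*Both arms, for the cost of the fix.* Leaving out both Cohort 1 sentinels gives 32 − 2 = 30 or 40 − 2 = 38 subjects.
- 30/6 × 0.05 × 0.5 = 0.13 to 38/3 × 0.10 × 0.5 = 0.63 scans with full attendance and acceptance.

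Subjects who leave before Day 7 and are replaced under Section 8.3 still count, because "The safety population will include all subjects who receive study drug". The extra subjects who replace them are not modelled. Nor is a sponsor stop of the whole study, which would take out every subject not yet at Day 43 together.

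**The case against.** The strongest case against is that the yield is close to nil and the remedy awkward. Section 6.3 concerns someone unable to finish the study. With a single dose, a subject willing to come back around Day 43 could largely have stayed in follow-up and had the planned scan. That leaves a scan at the exit visit, which may fall within days of dosing, when a negative result says little. This stands: few subjects will use the return route, and an exit scan is second best. It is still better than no scan, in a subject for whom the plan wanted one.

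A reader might infer that these subjects leave without safety assessment, or that MRI is barred. Neither is so. The exit visit includes a neurologic examination and AE review, the protocol contemplates an MRI when indicated, and SAP 6.4.2 puts unscheduled assessments in the listings. What is missing is a requirement to scan.

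A reader might also infer that the safety results are biased or that escalation is compromised. The documents do not support this. MRI is not among the named primary endpoints, SAP 8.7 only lists it, and the minimum data for escalation run to 7 days after dosing. A missing scan can also be found by cross-reading the age, disposition and MRI listings.

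Finally, the three protocol clarification letters cited in SAP 3.1 are not available. However, SAP Table 1, in a plan that names those letters as reference material, still shows no MRI in the early-termination column.

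**Conclusion.** The gap is real and follows directly from the schedule: under the stated rule, a consenting subject aged 50 or over who leaves before the Day 43 MRI and attends the exit visit loses the one ARIA scan planned for that subject. It is minor. On the assumed rates, 0.10 to 0.48 PMN310 subjects in the whole trial are recoverable with full attendance and acceptance, or about 0.05 to 0.39 if 50% to 80% attend and accept. Those figures rest entirely on assumed age mix, exit rate, consent share and attendance, and they count an early exit scan as a full recovery.

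The point should not be stretched to subjects under 50, who have no post-dose scan by design, or to subjects who withdraw consent, for whom no procedure is allowed. Nor does it show that the choice of Day 43 is wrong. It is a cheap improvement to subject safety and does not call any analysis into question.

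**What to change.** At the next amendment, add to Protocol Section 6.3, the 12/ET columns of Appendix 1 and SAP Table 1, and footnote 7: *Subjects aged ≥ 50 years who terminate before their Day 43 MRI and have not withdrawn consent will have that MRI at the early-termination visit, or in the Day 43 window (Day 40 to 46) if they are willing to return then.*

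In the same amendment, change > 50 to ≥ 50 in Section 6.2.2.4. The Day 43 list there excludes a subject aged exactly 50, whom Section 7.1.7 and footnote 7 include. Left alone, it would conflict with the new sentence.

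In the SAP 8.7 listing, show the actual study day of any early-termination scan. SAP 6.4.4 would otherwise assign it to the closest scheduled visit and hide how soon after dosing it was taken. A line marking subjects aged 50 or over with no post-dose MRI as not assessed is optional.

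**Cost.** No scan is added beyond the one already planned for that subject: about 0.1 to 0.6 scans across both arms on the assumptions above. A subject who returns makes one extra trip, and a negative scan within days of dosing is weak evidence of no ARIA. Section 11.3 requires that "A protocol amendment must receive IRB/IEC approval before implementation", so a change this small should be bundled with other changes and should not trigger an amendment of its own.

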7. DESCRIPTION OF STUDY PROCEDURES

Study assessments and procedures are to be performed on the schedule outlined in Appendix 1 and listed by visit in Section 6.

Additional details for selected study procedures are provided in the sections below.

7.1.1. Demography and Medical History

Relevant medical conditions, concomitant illness, surgeries within the 6 months before Screening should be documented. For female subjects, the last menstrual period should be recorded.

7.1.2. Columbia-Suicide Severity Rating Scale

The C-SSRS is an interview with the subject that systematically evaluates suicidal ideation and behavior. The C-SSRS (Baseline - Screening and Since Last Visit versions) will be performed by a qualified trained rater.

At Screening, the C-SSRS will be used to exclude any candidate with a history of suicide behavior or ideation. If responses ("yes" answers to Item 4 or 5) indicate that the candidate may have experienced suicidal ideation associated with actual intent or plan within 12 months of Screening, may have had a history of suicidal behavior within the past 5 years, or had any lifetime history of recurrent suicidal behavior, the candidate will be excluded from participation in the study.

After Screening, the C-SSRS will be used to assess ideation and behavior at visits specified in Appendix 1. If there is a "yes" answer to Item 4 or 5, or to any behavioral question, a suicidal risk assessment must be performed as soon as possible by a qualified mental health practitioner (with expertise in evaluation of suicidality) to determine whether it is safe for the subject to continue participation in the study.

7.1.3. Physical Examination

A full physical examination in this study will include the following: skin, eyes, ears, nose, oral mucosa, and throat, cardiac, respiratory, abdomen, and extremities.

A symptom-directed physical examination will include both a full physical examination and a directed examination of the affected system related to any reported AE.

Clinically relevant findings on the physical examination performed at Screening will be recorded as medical history. Any clinically relevant treatment emergent new finding on examination will be documented as an AE.

7.1.4. Neurological Exam

Neurological examinations will include the following: mental status, level of consciousness, cranial nerve function, sensory function, motor function, and reflexes.

Clinically relevant findings from the neurological examination performed at Screening will be recorded as medical history. Any clinically relevant treatment-emergent new finding on examination will be documented as an AE.

7.1.5. Vital Signs

Vital signs will include heart rate, respirations, blood pressure, and temperature. All vital signs should be measured after the subject has rested for 5 minutes in a supine position. The same position should be used throughout a subject's participation in the study.

